#### (4) Conversion rate to thoracotomy

Justification for selection: The need for conversion to thoracotomy due to failed thoracoscopic surgery

increases the risk to the subject. Therefore, the "conversion rate to thoracotomy" is selected as one of the effectiveness indicators of the product. At the same time, with reference to the *Guidelines for Technical Review of Endoscopic Stapler Registration* issued by NMPA (original CFDA) on March 13, 2017, the "conversion rate to thoracotomy" is selected as an effectiveness evaluation indicator for such products.

**Evaluation time:** During the surgery.

**Evaluation method:** The reasons for conversion to thoracotomy during thoracoscopic surgery are truthfully recorded. The common cases for conversion to thoracotomy are pulmonary artery bleeding, pulmonary vein bleeding, lymph node metastasis or lymph node calcification and adhesion, pulmonary artery anatomical deformity, and linear cutter stapler failure.

**Formula:** Rate of conversion to thoracotomy = number of eligible subjects in each group/total number of subjects in this group  $\times 100\%$ 

#### (5) Number of staple line repair needles

**Justification for selection:** When the stapler is used for pulmonary tissue anastomosis, the situation that the staple line needs to be repaired may occur. When the number of repair needles becomes larger, it may increase the risk to the subject. Therefore, the "number of stitches repaired with staple line" is selected as one of the indicators to evaluate the effectiveness of the product. At the same time, with reference to the *Guidelines for Technical Review of Endoscopic Stapler Registration* issued by NMPA (original CFDA) on March 13, 2017, the "number of stitches repaired by staple line" is selected as an effectiveness evaluation indicator for such products.

**Evaluation time:** During the surgery.

Evaluation method: The number of staple line repair needles of each subject during operation is recorded.

**Precautions:** ① Anastomotic repair is required when the anastomotic ring is incomplete, leaking and bleeding. Anastomotic repair may also be necessary when there is a dehiscence of the staple line during surgery. Sometimes the investigators may perform anastomotic repair in order to strengthen the anastomotic site. Therefore, the reasons for repair should be recorded; ② If the investigators use other devices for repair, it is necessary to record the product name and the quantity used, and finally replace the number of repair needles with the quantity used.

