#### 8.2.5.5 Other examinations

(1) Intraoperative observation items: operation starting time, operation ending time (24 h clock h/min) , anastomosis starting time, anastomosis ending time (s), resected lobe or segment , intraoperative blood

 Mainly record drugs that affect healing (e.g., antineoplastic agents, corticosteroids) or coagulation.

 Body mass index (BMI) = weight (kg)  $\div$  height (m^2)

 For laboratory examinations, the reports/results issued by our hospital within 7 days prior to surgery can be accepted.

 For imaging examination, the reports/results issued by our hospital within 1 month prior to surgery can be accepted.

 In case of air leakage and bleeding at the staple line, the investigators may decide whether the subject will receive

relevant examinations according to actual needs.

 The duration from the time of thoracotomy to chest closure is recorded.

 Right upper lobe, right middle lobe, right lower lobe, left upper lobe and left lower lobe.

loss, whether the transection and anastomosis are successful, whether the cutting staple line is complete, whether there is leakage in the cutting staple line, whether there is bleeding in the cutting staple line, whether there is air leakage in the staple line, whether there is conversion to thoracotomy , number of stitches for staple line repair , whether there is staple line dehiscence , whether there are other complications , evaluation on the stapler operating performance;

- (2) Use of device : models and specifications of electric-endoscopic stapler, reload models and specifications, device defect;
- (3) Postoperative follow-up observation: whether there is anastomotic line bleeding , whether there are other complications , duration of chest tube drainage (days), whether there is anastomotic infection;
- (4) Routine observation items: adverse events/serious adverse events, concomitant and combined medication, protocol deviations.

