## 8.2.7.1 1st visit 1/before surgery (Day $-7 \sim 0$ )

- (1) The ICF form shall be signed;
- (2) Screening subjects according to the inclusion and exclusion criteria;
- (3) Randomized grouping;
- (4) Recording demographic data, current medical history and past medical history are recorded;
- (5) Examining vital signs;
- (6) Performing preoperative imaging examination (CT/MRI examination);
- (7) Performing laboratory examinations (blood routine, coagulation routine, blood biochemistry, heart examination, pulmonary function test, arterial blood gas analysis, blood pregnancy test);

 If yes, please specify the reason and whether it is related to the stapler. If the investigators use other devices for repair, it is necessary to record the product name and the quantity used, and finally replace the number of repair needles with the quantity used.

 Truthfully record the model and amount used in the clinical trial.

 If corresponding symptoms occur, the reasons for confirming the event should also be briefly described, so as to facilitate the review. The diagnosis is confirmed by thoracoscopy or second surgical exploration.

- (8) Recording concomitant and concomitant medications;
- (9) Recording protocol deviations;

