# 9.7 Statistical Methods of Data, Together with Processing Methods of Missing, Unused or Wrong Data and Unreasonable Data

#### 9.7.1 Statistical method for data

Statistical analysis is performed using the SAS 9.1 software.

Statistical description on all data, including demographic data, baseline data, all efficacy indicators and all safety data shall be performed. Measurement data will be statistically described using mean, standard deviation, minimum, maximum, median, 25th percentile and 75th percentile; enumeration data will be statistically described using frequency and percentage.

The primary effectiveness evaluation indicator (device cutting and anastomosis success rate) is evaluated by the confidence interval method.

The secondary evaluation indicators are evaluated by the difference test. Measurement data are compared using two independent samples t-test. Enumeration data are compared using Pearson's  $X^2$  test or Fisher's

exact test.

The safety evaluation indicators are evaluated by the difference test. Measurement data are compared using two independent samples t-test. Enumeration data are compared using Pearson's  $X^2$  test or Fisher's exact test. The adverse events and device defects occur in this trial shall be shown in list.

The stapler operational performance is evaluated by the difference test, with the Pearson's  $X^2$  test or Fisher's exact test.

The central effect is considered in the analysis process. The general linear model is used for measurement data, and CMH is used for enumeration data.

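### The repair-needle endpoint swaps stitch counts for device counts without conversion, so its mean has no clear unit and can mislead if repair tools differ by arm

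*Combined protocol and SAP*

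**What the plan says.** Section 8.1.7.2 (5) makes the number of repair needles, also called stitches, a secondary effectiveness indicator: "The number of staple line repair needles of each subject during operation is recorded". It gives the count a direction: "When the number of repair needles becomes larger, it may increase the risk to the subject". The item collected under Section 8.2.5.5 is the "number of stitches for staple line repair".

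The precautions in the same section then change the unit for some subjects. If another device is used for repair, the investigator is to record it and "finally replace the number of repair needles with the quantity used". Footnote 10, attached to the intraoperative items of Section 8.2.5.5, says the same: "it is necessary to record the product name and the quantity used, and finally replace the number of repair needles with the quantity used".

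The section also recognises repairs that do not follow from a defect: "Sometimes the investigators may perform anastomotic repair in order to strengthen the anastomotic site". It asks for the reason for repair to be recorded.

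On analysis, Section 9.7.1 states "Measurement data will be statistically described using mean, standard deviation, minimum, maximum, median" and, for secondary indicators, "Measurement data are compared using two independent samples t-test". Section 9.5 sets the level at 0.05 and reads p > 0.05 as no significant difference.

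**The concern.** A stitch and a device unit are not the same quantity, and the plan gives no factor to turn one into the other. It also has no rule for a subject repaired with both, and no analysis by repair method. A mean taken over the two has no clear unit, whatever happens in the trial.

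The comparison between arms is a further matter. Section 8.2.4 says that investigators cannot be blinded, and the operator chooses how to repair. For chest-tube removal, Section 8.1.7.2 (3) brings in an investigator outside the subject's treatment to limit bias. The repair count has no such safeguard. If one arm is repaired more often with devices, the substituted score can create, hide or reverse a difference in repair burden. Because Section 9.5 treats p > 0.05 as no significant difference, a masked difference would read as reassurance.

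Reinforcement adds a smaller problem. The reason for repair is recorded but no planned analysis uses it, so elective strengthening counts the same as repair of a failed line.

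**Working it through.** The plan states no figure for this endpoint: no repair rate, no stitch number and no share of device repairs. There is nothing to reproduce, and the size of any distortion cannot be computed from the documents. What follows is illustration under stated assumptions. Only the sample sizes (82 per arm, or 65 evaluable, Section 9.2.1), the t-test (Section 9.7.1) and the 0.05 level (Section 9.5) come from the plan.

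**Step 1, hand count.** Assume 82 subjects per arm, 20 repaired in each, and every repair worth 4 stitches of work.

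- All repairs stitched: 20 × 4 / 82 = 80/82 = 0.98 per subject.
- Half of the repairs done with one device unit each: (10 × 4 + 10 × 1) / 82 = 50/82 = 0.61 per subject.
- Difference: 0.61 − 0.98 = −0.37, although the repair work is the same.

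**Step 2, equal repair need, simulated t-test.** Assume 82 per arm, 20% of subjects repaired in both arms, stitches per sutured repair = 1 + Poisson(2) (mean 3), and one unit for each device repair. The expected score is 0.20 × [(1 − f) × 3 + f × 1], where f is the share of repairs done with a device.

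| Device share, arm A vs arm B | Expected means, A vs B | t-test rejects |
|---|---|---|
| 50% vs 50% | 0.40 vs 0.40 | about 5% |
| 20% vs 0% | 0.52 vs 0.60 | about 6 to 7% |
| 50% vs 30% | 0.40 vs 0.48 | about 7% |
| 50% vs 0% | 0.40 vs 0.60 | about 18 to 19% |
| 100% vs 0% | 0.20 vs 0.60 | about 77 to 78% |

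The ranges are the spread between repeated runs.

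**Step 3, sensitivity to the assumptions.**

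- 10% repaired, 82 per arm: about 9 to 11% at 50% versus 0%, and about 35 to 37% at 100% versus 0%.
- 5% repaired, 82 per arm: about 5.5% at 50% versus 0%, and about 11% at 100% versus 0%.
- 20% repaired, 65 per arm: about 15% at 50% versus 0%, and about two thirds at 100% versus 0%.

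**Step 4, a real difference.** Assume that 30% of arm A and 15% of arm B need repair, with the same stitch model and 82 per arm.

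- All stitched: means 0.30 × 3 = 0.90 and 0.15 × 3 = 0.45. The t-test detects the difference in about 52 to 54% of trials.
- Half of arm A's repairs by device: mean 0.30 × (0.5 × 3 + 0.5 × 1) = 0.60 against 0.45. Detection falls to about 14%.
- All of arm A's repairs by device: mean 0.30 × 1 = 0.30 against 0.45. The arm with twice as many repairs now has the lower score.

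The direction is not fixed. It depends on which arm uses more devices and on how many device units stand in for how many stitches.

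**The case against.** The strongest reply is that a false difference needs unequal tool mixes and the documents show none. That stands. With equal mixes the test keeps its level, and mild imbalances or a low repair rate barely move it. The large figures come from assumed contrasts of 50% or 100% against none.

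This is also one of five secondary indicators, and the non-inferiority criterion in Section 9.5 uses only the success rate of cutting and anastomosis. A distorted repair score would not by itself hide device failure: line completeness, leakage, bleeding and dehiscence are recorded separately under Section 8.2.5.5, and dehiscence and air leakage have their own safety rates. Both points stand.

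Section 9.7.1 does not expressly class this count as measurement data, so the mean and t-test are the natural reading rather than a stated rule. Section 9.1 refers to a separate statistical analysis plan, but nothing supplied resolves the units.

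Section 8.2.8 prohibits products with similar efficacy, which may narrow the devices available for repair. Section 8.1.7.2 (5) nevertheless foresees other devices, so the two passages need to be reconciled.

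A reader might infer that the rule necessarily gives a wrong result for this endpoint, or that tool choice did differ by arm. The documents support neither. None of these points supplies the missing conversion: the substitution is written in two places and is not a matter of absent detail.

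**Conclusion.** The point holds as a defect in the definition of a secondary endpoint. The substitution puts stitches and device units into one score, so the mean lacks a clear meaning even when the comparison between arms is fair. The comparison can mislead if the mix of repair tools differs by arm, which unblinded choice of tool makes possible but does not establish.

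Under the assumptions shown, the effect ranges from almost none (about 5 to 7% rejection with equal or mildly different mixes) to severe (about 77 to 78% when one arm uses devices for every repair and the other for none). Those figures rest on an assumed repair rate, stitch number, device share and one unit per device repair, and serve only as illustration. A reader might also carry the concern over to the trial's main claim. That is not supported, because this indicator does not enter the non-inferiority decision.

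**What to change.** - Delete the substitution in Section 8.1.7.2 (5) and in footnote 10.
- Analyse stitches in stitches. Report other repair devices separately by arm, by product and quantity, and show subjects repaired with both in each table.
- Use the recorded reason to show reinforcement apart from repair of a defective line.
- Optionally add, as a supportive comparison, the proportion of subjects with any repair for a defect (incompleteness, leak, bleeding or dehiscence), by whatever tool. This should not replace the endpoint, which the protocol says was chosen with reference to a regulatory guideline. It is useful because a subject repaired only with a device will have no stitches, so the stitch count alone still depends on tool choice. The decision to repair also stays with the unblinded operator, so this comparison is not free of bias either.
- State in the statistical analysis plan how the stitch count is classed and tested.

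The cost is a wording change in two places and one or two more tables. Stitches, product name, quantity and reason for repair are already required, so no new data or subjects are needed.

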#### 8.1.8 Safety evaluation method

#### (1) Incidence of staple line dehiscence

**Justification for selection:** When stapler is used for pulmonary tissue anastomosis, it is necessary to select appropriate reload. Dehiscence of the staple line may increase the risk to the subject. Therefore, the "incidence of staple line dehiscence" is selected as one of the safety indicators of the product under evaluation. At the same time, with reference to the *Guidelines for Technical Review of Endoscopic Stapler*
*Registration* issued by NMPA (original CFDA) on March 13, 2017, the "incidence of staple line dehiscence" is selected as a safety evaluation indicator for such products.

**Evaluation time:** During the surgery.

Method of evaluation: Staple line dehiscence due to "staple popping" during surgery is recorded.

**Formula:** Incidence rate of staple line dehiscence = number of eligible subjects in each group/total number of subjects in the group  $\times 100\%$ 

## (2) Incidence of staple line bleeding

**Justification for Selection:** Staple line bleeding is a common complication of stapling procedures in lung tissue and increases the risk to the subject. Therefore, "the incidence of staple line bleeding" is selected as one of the indicators to evaluate the product safety. Meanwhile, with reference to the *Guidelines for Technical Review of Endoscopic Stapler Registration* issued by NMPA (original CFDA) on March 13, 2017, the "incidence rate of staple line bleeding" is selected as a safety evaluation indicator for such products.

Evaluation time: from the end of surgery to the end of follow-up.

**Evaluation mode:** Respiratory tract bleeding occurs after operation, and it is determined whether the bleeding is the source of anastomotic line by observing thoracic drainage tube, thoracoscopy and angiography. If the source is not clear, it is called respiratory tract bleeding.

Formula: Incidence rate of staple line bleeding = number of eligible subjects in each group/total number of subjects in the group  $\times 100\%$ 

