## (3) Incidence of air leakage

**Justification for selection:** Air leakage is a common complication of lung tissue anastomosis, which will increase the risk of subjects. Therefore, the "occurrence rate of air leakage" is selected as one of the safety indicators for product evaluation. At the same time, with reference to the *Guidelines for Technical Review of Endoscopic Stapler Registration* issued by China Food and Drug Administration on March 13, 2017, the "incidence rate of air leakage" is selected as a safety evaluation indicator for such products.

**Evaluation time:** During the surgery.

**Evaluation mode:** After the completion of cutting and anastomosis of lung tissues, the investigators drip normal saline to the staple line to see whether there are bubbles, which is used as the basis for judging air leakage.

Formula: Incidence of air leakage = number of subjects with air leakage/total number of subjects in the group  $\times 100\%$ 

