#### 8.2.5.4 Postoperative imaging examination 

- (1) Angiography: whether there is staple line bleeding;
- (2) Thoracoscopy: whether there is air leakage, whether there is staple line bleeding;

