- (16)Prolonged air leak: Air leaks from the rough surface of the lung after lobectomy or segmentectomy are common. With the expansion of the remaining lung and the elimination of the residual cavity, air leakage generally stops 2 to 3 days after surgery. If there is still air leakage more than 7 days after surgery, it is called "prolonged air leakage". The incidence after pneumonectomy is 15.2%. Although prolonged air leaks rarely cause other complications, the length of hospital stay will be prolonged by 5 to 6 days. The management of prolonged air leaks varies according to the condition, while the experience of thoracic surgeons also plays a significant role, with no single and fixed treatment mode. Increase or decrease the attraction force of closed thoracic drainage system, and install another thoracic drainage tube. Use medical glue to block the small bronchi of air leaking lung segment. Spraying fibrin glue on the rough surface of lung or spraying talc on thoracic cavity can be applied. The second thoracotomy is rarely require. However, if there is an infection in the thoracic cavity and there is a lot of air leakage,

bronchopleural fistula may occur. After the diagnosis of bronchopleural fistula is confirmed, reoperation is required.

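### The staple-line bleeding rate omits bleeding during surgery, although the trial records it; later air leaks and dehiscence reach the comparison only indirectly

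*Combined protocol and SAP*

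**What the plan says.** Section 8.1.8 gives each staple-line event one observation period.

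- **Bleeding, 8.1.8 (2).** The period is "from the end of surgery to the end of follow-up". The method also starts after the operation: "Respiratory tract bleeding occurs after operation, and it is determined whether the bleeding is the source of anastomotic line".
- **Air leakage, 8.1.8 (3).** The period is the operation. Investigators "drip normal saline to the staple line to see whether there are bubbles".
- **Dehiscence, 8.1.8 (1).** Staple popping "during surgery is recorded"; nothing later is counted.

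The data items do not follow the same split. The intraoperative items in Section 8.2.5.5 (1) include "whether there is bleeding in the cutting staple line". Postoperative thoracoscopy in Section 8.2.5.4 looks for "whether there is air leakage, whether there is staple line bleeding", but it is done at the investigator's discretion. The postoperative follow-up items in Section 8.2.5.5 (3) are bleeding, other complications, days of drainage and infection. Neither air leakage nor dehiscence has an item there.

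**The concern.** Whether the arms differ in these event rates is a stated secondary objective (Section 8.1.2), and Section 9.5 reads p > 0.05 as no significant difference. A bleeding rate that omits the period in which the stapler is fired is an incomplete basis for that comparison. No reason is given for excluding bleeding during surgery, although the trial looks for it and records it.

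Late air leaks and late dehiscence have the mirror problem in weaker form. Their rates stop when surgery ends, and later events can enter only through broader measures that do not isolate them. At stake is the completeness of the event-specific safety comparison. The primary non-inferiority test does not depend on it.

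**Working it through.** **1. The plan's own figure.** Section 9.2.1 uses 97% success in both arms, a margin of 10 points, one-sided alpha 0.025 and 80% power.

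- n3 = 2 × 0.97 × 0.03 × (0.842 + 1.960)² / 0.10² = 45.7.
- n4 = (n3/4) × [1 + √(1 + 4/(0.10 × n3))]² = 64.1, rounded up to 65.
- 65 / 0.80 = 81.25, rounded up to 82 per arm, 164 in all.

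The plan's 65, 82 and 164 reproduce. They rest on the primary endpoint, so a change to the safety indicators leaves them as they are.

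**2. Periods counted against items recorded.**

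| Event | Counted in its own rate | Recorded in the other period |
|---|---|---|
| Bleeding | After surgery only | Yes: own intraoperative item, 8.2.5.5 (1) |
| Air leakage | During surgery only | Conditionally: thoracoscopy if ordered (8.2.5.4), or as a complication or AE |
| Dehiscence | During surgery only | No own item: only as a complication or AE/SAE |

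The mismatch is clearest for bleeding, conditional for leakage and weakest for dehiscence.

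**3. Where an intraoperative bleed goes.** Take a bleed that is controlled without conversion.

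- *Bleeding rate, 8.1.8 (2):* not counted, because it precedes the end of surgery.
- *Primary endpoint, 8.1.7.1:* success requires complete lines with no leak and no bleeding; failure is persistent leak and bleeding with conversion required. This bleed fits neither definition cleanly.
- *Repair stitches, 8.1.7.2 (5):* counted if stitched, but pooled with repairs for leakage, incomplete lines, dehiscence and elective reinforcement. Reasons are recorded, but no comparison by reason is planned.
- *SAE and AE incidence, 8.1.8 (5) and (6):* staple-line adverse events are classed as SAEs, so it may appear here, pooled with all other events.

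None of these is a rate of staple-line bleeding.

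**4. Possible size.** The documents give no staple-line bleeding rate for either period. As an assumption only, let a = 2% to 10% be the intraoperative rate and b = 0.5% to 2% the postoperative rate, independent of each other. The either-period rate is u = 1 − (1 − a)(1 − b), and the share the indicator omits is 1 − b/u.

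| a | b | u | Counted per 82 | Either period per 82 | Omitted |
|---|---|---|---|---|---|
| 2% | 0.5% | 2.49% | 0.4 | 2.0 | 80% |
| 2% | 2% | 3.96% | 1.6 | 3.2 | 49% |
| 10% | 0.5% | 10.45% | 0.4 | 8.6 | 95% |
| 10% | 2% | 11.8% | 1.6 | 9.7 | 83% |

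**5. What so few events can show.** With 82 per arm and no events in one arm, the two-sided Fisher p-value is 2 × C(82,k)/C(164,k) for k events in the other. This gives 0.059 for k = 5 and 0.028 for k = 6. Significance therefore needs at least 0 against 6, while the assumed postoperative rates give fewer than 2 expected events per arm.

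**The case against.** The strongest reply is that the periods follow the methods of detection. A saline bubble test needs an exposed staple line; drain observation and angiography belong after the operation. Pooling the two mixes events found by different means and of different severity. That argument stands against a single pooled rate for leakage or dehiscence. It does not explain leaving out intraoperative bleeding, which has its own item and can be shown separately.

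A second reply is that the events are not lost. Drainage beyond 7 days is the plan's surrogate for healing, tube removal is judged by investigators outside the subject's care, and device-relatedness is examined in each such case. Repair stitches, AE incidence and SAE incidence are all compared between arms. This is right as far as it goes: the events can reach the safety comparison, but without an event-specific rate. The drainage indicator also misses leaks that stop sooner.

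Three stronger readings are tempting, and the documents do not support them.

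- *A repaired bleed is definitely not a primary failure.* The success wording excludes any bleeding, so the text leaves the case unresolved.
- *All the data needed are already on the CRF.* The CRF is not among the documents, and Section 8.2.5.5 lists no postoperative item for leakage or dehiscence.
- *About 12 of 82 subjects per arm have a leak that the indicator cannot count* (0.152 × 82 = 12.5). Section 14.1.5 (16) says "The incidence after pneumonectomy is 15.2"%. That is leak beyond 7 days after a different operation, in an item about the raw lung surface rather than the staple line. Such subjects would be expected to appear under drainage beyond 7 days, and some may already have leaked during surgery.

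**Conclusion.** The point holds for bleeding. Followed as written, the bleeding comparison omits intraoperative events that the trial records, and no other planned analysis supplies that rate. For air leakage and dehiscence the finding is narrower: later events reach the comparison only indirectly, and their capture is not systematic.

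The size cannot be fixed from the documents. The 49% to 95% range rests wholly on the assumed rates and on independence between the periods; it shows that the omitted share could be large, not what it is. A reader might also infer that the omission favours the test device. Nothing in the documents shows this: the same periods apply to both arms, and the effect shown here is fewer countable events in each. The sample size and the non-inferiority margin are untouched. The unclear status of a controlled bleed in Section 8.1.7.1 does bear on the primary endpoint and needs to be settled there.

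**What to change.** Before the SAP is finalised (Section 9.1 puts this before database lock):

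1. Define the bleeding indicator to include the recorded intraoperative item, and report intraoperative, postoperative and either-period bleeding by arm.
2. Keep the intraoperative rates of air leakage and dehiscence. Add a separate by-arm table of postoperative events taken from AE/SAE and complication records, and from thoracoscopy where it was done. State that this ascertainment is not systematic.
3. State in Section 8.1.7.1 how a bleed controlled without conversion is classified for the primary endpoint.

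No new procedure is needed and the sample size does not change. The costs are a higher stated bleeding rate in both arms and a little more tabulation. Timing matters, because Section 9.8 treats statistical analyses added outside the SAP as exploratory only.
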